## **7.2 Serious adverse events**

To ensure patient safety, every SAE, regardless of causality, occurring during following time periods must be reported to Novartis within 24 hours of learning of its occurrence:

- after the subject has provided informed consent and until 12 weeks after the last administration of study treatment or 30 days after the subject has stopped the study participation (defined as last visit of the study at Week 268) for subjects who don't enter follow-up 2 period
- after the subject has provided informed consent and until the last telephone contact for patients who enter follow-up 2 period

Any SAEs experienced after these periods should only be reported to Novartis if the investigator suspects a causal relationship to study treatment.

Recurrent episodes, complications, or progression of the initial SAE must be reported as follow-up to the original episode, regardless of when the event occurs. This report must be submitted within 24 hours of the investigator receiving the follow-up information. An SAE that is considered completely unrelated to a previously reported one should be reported separately as a new event.

Information about all SAEs (either initial or follow-up information) is collected and recorded on the paper Serious Adverse Event Report Form (SAE report form) or where available the Serious Adverse Event Form within the remote data capturing (RDC) system. The investigator must assess the relationship to each specific study treatment and complete the paper or electronic SAE report form in its entirety in English.

When SAEs are recorded on the paper SAE form, these should be faxed **within 24 hours of awareness of the SAE** to the local Novartis Drug Safety and Epidemiology (DS&E) Department. The telephone and fax number of the contact persons in the local department of DS&E, specific to the site, are listed in the investigator folder provided to each site. The original copy of the SAE Report Form and the fax confirmation sheet must be kept with the case report form documentation at the study site.

When SAEs are recorded electronically in the Oracle Clinical/ Remote Data Capture (OC/RDC) system, these should be entered, saved and e-signed **within 24 hours of awareness of the SAE**. These data will automatically be submitted to Novartis DS&E immediately after investigator signature or 24 hours after entry, whichever occurs first.

The Investigator must assess the relationship to the study treatment.

Note that any follow-up information provided should describe whether the event has resolved or continues, if and how it was treated, whether the blind was broken or not and whether the subject continued or withdrew from study participation. Each re-occurrence, complication, or progression of the original event should be reported as a follow-up to that event regardless of when it occurs.

If the SAE is not previously documented in the IB or Package Insert (new occurrence) and is thought to be related to the study treatment, a DS&E Department associate may urgently require further information from the investigator for Health Authority reporting. Novartis may need to issue an Investigator Notification (IN) to inform all investigators involved in any study with the same investigational treatment that this SAE has been reported. Suspected Unexpected Serious Adverse Reactions (SUSARs) will be collected and reported to the competent authorities and relevant ethics committees in accordance with Directive 2001/20/EC or as per national regulatory requirements in participating countries.

### **7.3 Pregnancy reporting**

To ensure subject safety, each pregnancy occurring while the subject is on study treatment must be reported to Novartis within 24 hours of learning of its occurrence. The pregnancy should be followed up to determine outcome, including spontaneous or voluntary termination, details of the birth, and the presence or absence of any birth defects, congenital abnormalities, or maternal and/or newborn complications.

Pregnancy should be recorded on a Clinical Trial Pregnancy Form and reported by the investigator to the local Novartis DS&E Department. Pregnancy follow-up should be recorded on the same form and should include an assessment of the possible relationship to the study treatment

Any SAE experienced during pregnancy must be reported on the SAE Report Form.

## **7.4 Data Monitoring Committee**

A data monitoring committee (DMC) will review the safety data of this trial at selected time intervals at least until the Week 68 PEA. Details regarding the DMC process will be available in relevant secukinumab DMC charter.

## **8 Data review and database management**

### **8.1 Site monitoring**

Before study initiation, at a site initiation visit or at an investigator's meeting, a Novartis representative will review the protocol and eCRFs with the investigators and their staff. During the study, the field monitor will visit the site regularly to check the completeness of subject records, the accuracy of entries on the eCRFs, the adherence to the protocol and to Good Clinical Practice, the progress of enrollment, and to ensure that study treatment is being stored, dispensed, and accounted for according to specifications. Key study personnel must be available to assist the field monitor during these visits.

The investigator must maintain source documents for each subject in the study, consisting of case and visit notes (hospital or clinic medical records) containing demographic and medical information, laboratory data, electrocardiograms, and the results of any other tests or assessments. All information on eCRFs must be traceable to these source documents in the subject's file. The investigator must also keep the original ICF signed by the subject and a signed copy is given to the subject.

The investigator must give the monitor access to all relevant source documents to confirm their consistency with the eCRF entries. Novartis monitoring standards require full verification for the presence of informed consent, adherence to the inclusion/exclusion criteria, documentation of SAEs, and of data that will be used for all primary and safety variables. Additional checks of the consistency of the source data with the eCRFs are performed according to the study-specific monitoring plan. No information in source documents about the identity of the subjects will be disclosed.

### **8.2 Data collection**

Designated investigator staff will enter the data required by the protocol into the OC/RDC system. Designated investigator site staff will not be given access to the system until they have been trained.

Automatic validation procedures within the system check for data discrepancies during and after data entry and, by generating appropriate error messages, allow the data to be confirmed or corrected online by the designated investigator site staff. The investigator must certify that the data entered into the eCRFs are complete and accurate. After database lock, the investigator will receive copies of the subject data for archiving at the investigational site.

### **8.3 Database management and quality control**

Novartis staff [or CRO working on behalf of Novartis] review the data entered into the eCRFs by investigational staff for completeness and accuracy and instruct the site personnel to make

any required corrections or additions. Novartis personnel will not make any corrections or additions to the data. Queries are sent to the investigational site using an electronic data query. Designated investigator site staff is required to respond to the query and confirm or correct the data. If the electronic query system is not used, a paper Data Query Form will be faxed to the site. Site personnel will complete and sign the faxed copy and fax it back to Novartis staff that will make the correction to the database. The signed copy of the Data Query Form is kept at the investigator site.

Concomitant medications entered into the database will be coded using the World Health Organization (WHO) Drug Reference List, which employs the Anatomical Therapeutic Chemical classification system. Concomitant procedures, non-drug therapies and AEs will be coded using the Medical dictionary for regulatory activities (MedDRA) terminology.

Laboratory samples will be processed centrally and the results will be sent electronically to Novartis (or a designated CRO).

ECG readings will be processed centrally and the results will be sent electronically to Novartis (or a designated CRO).

Subjects will use electronic pens to enter data on HRQoL tools. This data will be processed centrally and the results will be sent electronically to Novartis (or a designated CRO).

Randomization codes and data about all study treatment dispensed to the subject and all IVR recorded dosage changes will be tracked using an IRT. The system will be supplied by a vendor, who will also manage the database. The database will be sent electronically to Novartis (or a designated CRO).

Each occurrence of a code break via IRT will be reported to the clinical team and monitor. The code break functionality will remain available until study shut down or upon request of Novartis.

## 9 Data analysis

Treatment groups for analysis will include:

- **Subjects who were PASI 75 responders at Week 52**
  - Secukinumab 150 mg
  - Secukinumab 300 mg
  - Placebo (secukinumab 150 mg in core studies)
  - Placebo (secukinumab 300 mg in core studies)
- **Subjects who were re-treated after relapse with secukinumab 150 mg or 300 mg**
  - Secukinumab 150 mg
  - Secukinumab 300 mg

- Subjects who were partial responders at Week 52
  - Secukinumab 150 mg
  - Secukinumab 300 mg

For open-label period analyses subjects being switched from 150 mg to 300 mg will be summarized as well.

NOTE: Week 52 assessments refer to Baseline extension assessments

## 9.1 Analysis sets

The following analysis sets will be used in this trial:

**Randomized set:** The randomized set will be defined as all subjects who were randomized. Unless otherwise specified, mis-randomized subjects (mis-randomized in IRT) will be excluded from the randomized set. Mis-randomized subjects will be defined as those subjects where IRT contact is made by the site either prematurely or inappropriately prior to confirmation of the subject's final randomization eligibility and double-blind study treatment was not administered to the subject.

**Full analysis set (FAS):** The FAS will be comprised of all subjects from the randomized set to whom study treatment has been assigned. Following the intent-to-treat principle, subjects will be analyzed according to the treatment assigned to at randomization, but actual stratum, if stratified randomization is used.

**Safety set:** The safety set includes all subjects who took at least one dose of study treatment during the treatment period. Subjects will be analyzed according to treatment received.

## 9.2 Subject demographics and other baseline characteristics

### Demographics and baseline characteristics

Summary statistics will be presented for continuous demographic and baseline characteristic variables for each treatment group and for all subjects in the randomized set. The number and percentage of subjects in each category will be presented for categorical variables for each treatment group and all subjects.

### Medical history

Any significant prior or active medical condition at the time of signing informed consent will be coded using the MedDRA dictionary. These medical conditions will be summarized by primary system organ class and preferred term.

To establish a baseline level of cardiovascular risk, the number and percentage of subjects with pre-solicited cardiovascular risk factors will be summarized by treatment group. The number of cardiovascular risk factors that each subject has will also be summarized by treatment group. If it is unknown whether or not a subject currently or previously experienced a specific cardiovascular risk factor, it will be assumed that cardiovascular risk factor did not occur for that subject.

Psoriasis specific medical history will be summarized by treatment group. Previous treatments for psoriasis and whether or not response was achieved will be summarized by treatment group. All the medical history information will be retrieved from the core studies.

## **9.3 Treatments**

### **Study treatment**

The analysis of study treatment data will be based on the safety set.

The duration of exposure to study treatment will also be summarized by treatment group. In addition, the number and percentage of subjects with cumulative exposure levels (e.g., any exposure,  $\geq 1$  week,  $\geq 2$  weeks,  $\geq 3$  weeks,  $\geq 4$  weeks,  $\geq 8$  weeks, etc.) will be presented.

### **Prior and concomitant medication**

Prior and concomitant medications will be summarized in separate tables by treatment group.

Prior medications are defined as treatments taken and stopped prior to first dose of study treatment. Any medication given at least once between the day of first dose of randomized study treatment and the date of the last study visit will be a concomitant medication, including those which were started pre-baseline and continued into the period where study treatment is administered.

Medications will be presented in alphabetical order, by Anatomical Therapeutic Classification (ATC) codes and grouped by anatomical main group. Tables will show the overall number and percentage of subjects receiving at least one treatment of a particular ATC code and at least one treatment in a particular anatomical main group.

Significant prior and concomitant non-drug therapies and procedures will be summarized by primary system organ class and MedDRA preferred term.

The number and percentage of subjects receiving different classes of prior psoriasis therapy (biologic systemic therapy, non-biologic systemic therapy, topical, phototherapy, photochemotherapy) will be presented by treatment group as well as the reasons for stopping their previous prior psoriasis therapies (primary lack of efficacy, secondary lack of efficacy, lack of tolerability, other) and the total duration of exposure to psoriasis therapies previously.

Prior concomitant medications will be retrieved from the core studies.

## **9.4 Analysis of the primary variable**

### **9.4.1 Variable**

The primary variable is the cumulative rate of subjects who lost PASI 75 response up to Week 68 (time=0 being defined as Week 52).

#### 9.4.2 Statistical model, hypothesis, and method of analysis

The statistical hypotheses are that the cumulative rate for subjects who lost PASI 75 response up to Week 68 are not different between secukinumab 150 mg and corresponding placebo as well as between secukinumab 300 mg and corresponding placebo.

Let  $p_j(t)$  denote the proportion of PASI 75 responders at time  $t$  for treatment group  $j$ , and let  $p_{0,j}(t)$  denote the proportion of PASI 75 responders at time  $t$  for placebo group  $j, j=1, 2$ , where

- $0_j$  corresponds to placebo (secukinumab 150 mg in core studies) for  $j=1$  and to placebo (secukinumab 300 mg in core studies) for  $j=2$ ,
- 1 corresponds to secukinumab 150 mg,
- 2 corresponds to secukinumab 300 mg.

The following hypotheses will be tested for  $52 \text{ weeks} \leq t \leq 68 \text{ weeks}$

- $H_1: p_1(t) - p_{0,1}(t) = 0$  versus  $H_{A1}: p_1(t) - p_{0,1}(t) \geq 0$ ,
- $H_2: p_2(t) - p_{0,2}(t) = 0$  versus  $H_{A2}: p_2(t) - p_{0,2}(t) \geq 0$ ,

In other words

- $H_1$ : Secukinumab 150 mg is not different from placebo with respect to the cumulative rate for subjects who lost PASI 75 response up to Week 68
- $H_2$ : Secukinumab 300 mg is not different from placebo with respect to the cumulative rate for subjects who lost PASI 75 response up to Week 68

Number and percentage of subjects with loss of PASI 75 response based on the number of subjects in the full analysis set at risk as denominator will be provided by treatment group.

For loss of PASI 75 response, between-treatment differences will be evaluated using a log-rank test, stratified by geographical region and body weight stratum, to compare the survival functions between secukinumab treatment groups versus placebo. The hazard ratios for these comparisons for loss of PASI 75 response and their corresponding 95% confidence intervals will be computed using a stratified Cox proportional hazards regression model with treatment group, core study and baseline PASI of core study and baseline PASI of extension study as explanatory variable and stratified by geographical region and body weight stratum. The primary analysis will be the log-rank test. Subjects who have not lost PASI 75 response up to Week 68 will be considered as censored observations.

The Kaplan-Meier estimates of the (1 minus cumulative rate loss of PASI 75 response) for each treatment will be plotted. The plot will include the number of subjects at risk for each treatment group at pre-specified time points (e.g., visits).

The number of subjects with loss of PASI 75 response, number of subjects in the analysis set, estimate of cumulative rate up to Week 68, median event time, and its estimated standard error, as estimable will be provided for each treatment group. In addition, for pre-specified time intervals (e.g., 4-week intervals) the following will be presented:

- for each treatment group and time interval: subjects at risk, subjects with loss of PASI 75 response, subjects with loss of PASI 75 response divided by subjects at risk, cumulative subjects with event and cumulative event probability including 95% confidence interval.

[figure not shown]
- for treatment comparisons the hazard ratio derived via Cox regression as well as log-rank test and Wilcoxon test.

Separate analyses will be performed for comparison of 150 mg secukinumab with placebo and 300 mg secukinumab with placebo. The two placebo groups will not be pooled for this analysis.

### Testing strategy

The familywise error will be set to  $\alpha=2.5\%$  (one-sided). The two hypotheses  $H_1$  (referring to 150 mg) and  $H_2$  (referring to 300 mg) will be tested at  $\alpha/2=1.25\%$  one-sided. In case, a null hypothesis has been rejected for one dose, but not for the other dose, the alpha can be shifted to the other dose and the null hypotheses can be retested at level  $\alpha=2.5\%$  (one-sided). The graphical approach of [Bretz et al (2009)] for sequentially rejective testing procedures is used to illustrate the testing strategy (Figure 9-1):

**Figure 9-1** Testing strategy

Other secondary endpoints will not be included in the testing strategy.

### 9.4.3 Handling of missing values/censoring/discontinuations

For the primary analysis subjects who did not lose PASI 75 response before Week 68 but with missing values at Week 68 will be considered as censored. Other time-to-event analyses will be handled analogously.

For other analyses (not time to event) missing values with respect to response variables based on PASI score and IGA mod 2011 score will be imputed with non-response regardless of the reason for missing data (e.g., premature study discontinuation, missed visit, administrative issues).

Following the intent-to-treat principle for subjects who prematurely discontinue treatment, but who are observed in the follow-up period, efficacy data collected in follow-up periods will be linked to planned but missed study visits as well, following imputation schemes described in the analysis plan (e.g., if a subject discontinues treatment at Week 56, but has follow-up visit F4, the PASI score observed at Visit F4 might be used for Week 60 assessments).

The last observation carried forward method will be applied to PASI score and IGA mod 2011 score. Note, that responses based on PASI score or IGA mode will be imputed differently as described above.

If all post Randomization Visit efficacy values are missing for one efficacy parameter then these missing values will not be imputed and this subject will be removed from the analysis of the corresponding variable, *i.e.*, it might be that the number of subjects providing data to an analysis

is smaller than the number of subjects in the FAS. In addition, missing baseline values will not be imputed.

#### **9.4.4 Supportive analyses**

Sensitivity analyses will be performed as follows:

- Subjects fulfilling at least one of the following criteria will be classified as non-responders with respect to PASI 75 and IGA 0 or 1 response at Week 68 and the Cox proportional hazards regression analysis of the primary analysis will be repeated:
  - subjects with missing injection (s) up to Week 68,
  - dropouts due to AEs, unsatisfactory therapeutic effect up to Week 68, and
  - subjects with missing data at Week 68.
- PASI 75 will be evaluated using Cox proportional hazards regression as described above with multiple imputations instead of non-responder imputation for missing values. Within this analysis the PASI score will be imputed and response variables will be derived based on the imputed scores. For each treatment group values will be imputed separately. Further details will be given in the analysis plan.

In addition, the secukinumab treatment groups will also be compared, i.e. a Cox proportional hazards regression will be fitted as described above including all four treatment groups. Placebo (secukinumab 150 mg in core studies) and Placebo (secukinumab 300 mg in core studies) will be compared as well as secukinumab 150 mg and secukinumab 300 mg.

### **9.5 Analysis of secondary variables**

#### **9.5.1 Efficacy variables**

##### **Subjects who were PASI 75 responders at Week 52**

##### **PASI 50, PASI 75, PASI 90, PASI 100 and IGA 0 or 1 response over time**

Summary statistics for PASI 50, PASI 75, PASI 90, PASI 100 and IGA 0 or 1 response by visit will be presented in contingency tables and will include absolute and relative frequencies. Confidence intervals for response rates will be derived as well based on the score method including continuity correction ([Newcombe, 1998](#)).

For PASI 50, PASI 75, PASI 90, PASI 100 and IGA 0 or 1 response at each visit, each secukinumab dose regimen will be compared to placebo (up to last visit with more than 5% of subjects in placebo group) by means of the stratified Cochran-Mantel-Haenszel-test as well as by means of a logistic regression model with treatment group, geographical region, body weight stratum, and baseline PASI as effects.

For PASI 50, PASI 75, PASI 90 and IGA 0 or 1 response the placebo-adjusted response rates including 95% confidence interval (based on normal approximation) will be derived by visit. Figures will be provided as well displaying estimates for responder rates by treatment including confidence intervals.

Subjects that were re-randomized at Week 52, hence who PASI 75 responder will be split into two subgroups based on the IGA 0 or 1 response at Week 52. For each of these subgroups summary statistics for PASI 50, PASI 75, PASI 90, PASI 100 and IGA 0 or 1 response by visit will be presented in contingency tables and will include absolute and relative frequencies.

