## 9.7 Sample size calculation

**Assumptions for the number of subjects eligible for randomized withdrawal (i.e for the analysis of primary endpoint):**

- Drop-out rate on secukinumab at Week 12 in core studies: 5% (estimate from CAIN457A2211)
- Drop-out rate on placebo at Week 12 in core studies: 15% (from CAIN457A2211)
- Placebo PASI 75 response rate at Week 12: 5% (conservative assumption)
- Drop-out rate on secukinumab up to Week 52 in core studies: 15% (common for secukinumab induction and placebo induction regimens, as in [Leonardi et al, 2008](#))
- PASI 75 response rate at Week 52 on secukinumab 150 mg in core studies: 65% (from dosing rationale in protocols of core studies) (power would be larger for 300 mg if we would assume similar loss of PASI75 rates)
- Type-I-error rate is defined to one-sided 2.5%

With these assumptions it is estimated to have 414 subjects eligible per dose to enter the randomized withdrawal, with a randomization ratio of 2:1 this would be 276 subjects on 150 mg and 138 subjects on placebo. With about 400 subjects the study would have more than 90% power to detect differences in the cumulative rates if 10% of subjects on secukinumab lost PASI 75 response versus 23% on placebo, PASS 2008 software (Log Rank Survival Power Analysis - Simple).

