# 1 Statistical methods planned in the protocol and determination of sample size

Data will be analyzed by Novartis using SAS according to the data analysis section 9 of the study protocol which is available in Appendix 16.1.1 of the CSR. Important information is given in the following sections and details are provided, as applicable, in Appendix 16.1.9 of the CSR.

Novartis	Confidential	Page 9
RAP Module 3	9-Apr-2018 (1:15)	Secukinumab / AIN457A2302E1

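### The by-visit 95% CI for the response difference from placebo uses a normal approximation that under-covers when rates are near 100%, and would do so badly if few placebo subjects remain in the denominator

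*Protocol*

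**What the plan says.** Protocol 9.5.1, for subjects who were PASI 75 responders at Week 52, plans three things by visit.

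- Single-arm rates: "Confidence intervals for response rates will be derived as well based on the score method including continuity correction".
- Comparison with placebo by a stratified Cochran-Mantel-Haenszel (CMH) test and a logistic regression, "up to last visit with more than 5% of subjects in placebo group".
- For PASI 50, 75, 90 and IGA 0 or 1, the difference from placebo: "the placebo-adjusted response rates including 95% confidence interval (based on normal approximation) will be derived by visit". The visit limit is not repeated in this sentence, and the form of the variance is not given.

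Protocol 9.7 gives the planned numbers per dose: "with a randomization ratio of 2:1 this would be 276 subjects on 150 mg and 138 subjects on placebo".

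SAP section 1 says "Data will be analyzed by Novartis using SAS according to the data analysis section 9 of the study protocol", and its list of changes (1.1.1) does not mention this interval. SAP 1.9.6, which sets out the randomized-withdrawal re-run, repeats the single-arm score intervals, the CMH test and the logistic model. It does not list the difference from placebo or its interval, and neither does the methods overview table in 1.9.1.3.

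**The concern.** The plan uses a well-behaved method for the single rates and a weaker one for the treatment contrast, without giving a reason. The normal-approximation interval takes its width from the observed proportions, so an arm at 100% contributes no variance at all. The design makes such results likely. By Protocol 3.2 only PASI 75 responders enter randomized withdrawal, so PASI 75 and PASI 50 are 100% in both arms at Week 52. Later, if subjects who relapse drop out of the denominator, the placebo arm could become very small.

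At stake is whether intervals labelled 95% in a stated secondary objective have roughly that coverage, and whether some exclude zero when the data do not support a difference.

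**Working it through.** **Inputs.** 414 subjects per dose at 2:1 gives 414 x 2/3 = 276 and 414/3 = 138, as the protocol states. The planning scenario is "10% of subjects on secukinumab lost PASI 75 response versus 23% on placebo" by Week 68. It gives a hazard ratio of ln(0.90)/ln(0.77) = 0.403 and a Schoenfeld power of 90.0% at 400 subjects and 91.0% at 414 (one-sided 2.5%). That agrees with the stated power of more than 90%, so these rates are used below as the plan's own. Protocol 3.3 predicts loss of PASI 75 on placebo of about 10% per month, and full relapse reaching 10% after four months. The plan gives no PASI 50 rates. If the relapse figure is taken as a rough guide to loss of PASI 50 and spread evenly (an assumption), retention after one month is 0.90^(1/4) = 97.4%.

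**Planned interval**, taken as the unpooled (Wald) form, with d = p1 - p0:

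d ± 1.96 x sqrt[p1(1-p1)/n1 + p0(1-p0)/n0]

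**Alternative**, the Newcombe hybrid score, with Wilson limits (l, u) per arm and no continuity correction:

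lower = d - sqrt[(p1-l1)² + (u0-p0)²]; upper = d + sqrt[(u1-p1)² + (p0-l0)²]

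**Coverage** is the sum, over all pairs of counts, of the product of the two binomial probabilities for those pairs whose interval contains the true difference.

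| Secukinumab vs placebo, n | True rates | Normal approx. | Hybrid score |
|---|---|---|---|
| 276 vs 138 | 99% vs 99% | 91.8% | 97.7% |
| 276 vs 138 | 98% vs 98% | 92.0% | 96.4% |
| 276 vs 138 | 99% vs 97% | 91.1% | 96.5% |
| 276 vs 138 | 95% vs 95% | 94.4% | 95.5% |
| 276 vs 138 | 97.4% vs 90% (PASI 75, first visit) | 93.9% | 95.2% |
| 276 vs 138 | 90% vs 77% (PASI 75, Week 68) | 94.7% | 95.1% |
| 200 vs 7 | 85% vs 85% | 66.8% | 95.4% |
| 200 vs 7 | 90% vs 90% | 51.8% | 95.7% |
| 200 vs 14 | 90% vs 90% | 76.5% | 96.2% |
| 200 vs 28 | 90% vs 90% | 90.7% | 96.0% |

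In the first-visit PASI 75 row, 97.4% is the planned 10% loss on secukinumab over four 4-week intervals, 0.90^(1/4), and 90% is the 10%-per-month loss on placebo. The 7 comes from 5% of 138 = 6.9, so more than 5% means at least 7. The 200 is an assumption; from 100 to 276 the coverage at a 90% rate stays at about 52%.

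**Single results, 276 vs 138.**

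- 276/276 vs 138/138: both variance terms are zero, so the interval is 0 to 0. Hybrid score: -1.4 to +2.7 points.
- 272/276 vs 138/138: d = -1.45 points. The standard error is sqrt(0.9855 x 0.0145/276) = 0.72 points, from the secukinumab arm alone. Interval: -2.86 to -0.04, which excludes zero. Fisher p = 0.31. Hybrid score: -3.7 to +1.4.

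**Single result, few placebo subjects.** 170/200 vs 7/7 gives -19.9 to -10.1 points; the hybrid score gives -20.6 to +20.7, and Fisher p = 0.60.

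**Direction.** With equal rates of 99% (276 vs 138), zero is wrongly excluded against secukinumab 7.5% of the time and in its favour 0.6%. At 98% the figures are 6.9% and 1.2%. Placebo is the smaller arm, so by chance it reaches 100% more often.

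**The case against.** Several stronger readings are tempting, and the documents do not support them.

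- *Late visits will have as few as 7 placebo subjects.* This requires relapsed subjects to leave the denominator. The 5% limit suggests a shrinking denominator, but it belongs to the CMH and logistic sentence. Protocol 9.4.3 imputes missing response as non-response whatever the reason, and SAP 1.9.4.1 does so at any randomized-withdrawal visit without data up to Week 156. On that reading the placebo n stays near 138, and coverage is about 94.5% at 80% vs 5% and 94.8% at 60% vs 10%.
- *The intervals are too narrow throughout.* This is true at boundary results only. With 7 placebo subjects and rates of 50%, the planned interval is wider on average than the hybrid score (69 vs 58 points), yet still covers only 87.6%. For 276/276 vs 135/138 it is the more cautious one: -0.3 to +4.6 points, against +0.2 to +6.2 (Fisher p = 0.036).
- *The method exaggerates efficacy.* The false exclusions run mostly the other way.
- *The difference is the only effect measure.* The logistic model can supply an odds ratio.

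It is also fair to say that PASI 90 and IGA 0 or 1 do not start at 100% by design, that coverage is close to nominal at the planned PASI 75 rates, and that the testing strategy in Protocol 9.4.2 excludes secondary endpoints. These points limit the consequence. They do not defend the method where rates are near 100%, and that case does not depend on the denominator question.

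**Conclusion.** The concern holds in limited form. For PASI 50, and for PASI 75 at the first visits, observed rates at or near 100% give a nominal 95% interval with about 91-92% coverage at the planned sample size, and a meaningless zero-width interval at 100% in both arms. For PASI 75 at the plan's own loss rates the shortfall is about one percentage point or less (93.9% and 94.7%). A severe shortfall, to about 52-67% at rates of 85-90%, arises only if relapsed subjects leave the denominator and about 7 placebo subjects remain, and the plan does not settle this.

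The figures assume the unpooled variance, the planned 276 and 138, and the response rates shown; rates of 97-99% for PASI 50 are an assumption. These are descriptive secondary outputs beside the CMH test and logistic regression, so neither the primary conclusion nor the error control is affected. It is also unclear whether the interval survives into the randomized-withdrawal re-run: the SAP's general reference to protocol section 9 implies that it does, while SAP 1.9.6 omits it.

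**What to change.** In Protocol 9.5.1, replace the normal approximation with the Newcombe hybrid-score interval for a difference of two proportions, or the Miettinen-Nurminen interval. Apply to it the same placebo-size limit on visits that already governs the CMH and logistic comparisons, and say whether relapsed subjects stay in the denominator, since the limit depends on that.

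In SAP 1.9.6, state whether the difference and its interval are kept for the randomized-withdrawal re-run. If they are kept, name the same score method; if they are dropped, record that in SAP 1.1.1.

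The cost is a few lines of text and a standard software option, with no new data. Some intervals become wider.
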